This proposed research will develop and pilot a somatically-oriented mindfulness curriculum designed to reduce the symptoms of occupational-based secondary trauma (ST) among victim service providers working in Montana. The content of the curriculum will be based on our previously published text *Secondary Trauma in the Workplace: Tools for Awareness, Self-Care, and Organizational Response in Montana* we wrote with a group of seven local victim service providers. The curriculum for this intervention, however, will be expanded to more fully include mindfulness meditation and somatic-based trauma resolution techniques.

The intervention curriculum will be developed and tested with three cohorts.

For the **first cohort**, Drs. [name] and [name] will pilot the curriculum in an undergraduate course in the Fall of 2019 (n= approximately 15 students). [name] will be the instructor of record. The content and effectiveness of the course will be evaluated using a survey. The complete survey and consent form are included in this application. There will be three waves of survey data collected. For the first two waves, students will be asked to complete the survey during the semester (wave one, during the first few weeks of class and wave two during the final few weeks of class). Students can choose not to complete the survey with no penalty. If at least 85%

of the students in each class participate in data collection waves one and two, all students will be eligible for some form of extra credit and/or participation in some kind of celebration (such as pizza on the last day of class). All students will be eligible, even if they themselves did not participate. A third wave may also be collected approximately one month after the course. Participation for this final wave of data collection will be incentivized by a \$20 e-gift card. Students' participation will be strictly optional.

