Work Demographics*	WD	7
Maslach Burnout Inventory – General Version*	MBI-G	16
Maslach Burnout Inventory – General Student Version*	MBI-GS	17
Maslach Burnout Inventory – Student Version*	MBI-S	16
Secondary Traumatic Stress Scale	STSS	18
The PTSD Checklist for DSM-5	PCL-5	20
Body Mass Index	BMI	2
Health Related Quality of Life	HRQoL	4
Autoimmune Diagnosis	AD	1
Patient Health Questionnaire – Somatic Symptom Severity	PHQ-15	15
AUDIT Alcohol Questionnaire	AUDIT	10
Tobacco, Alcohol, Prescription and Other Substance Use Tool	TAPS	4
Jenkins Sleep Scale	JSS	4
Generalized Anxiety Disorder	GAD-7	7
Patient Health Questionnaire – Depression	PHQ-8	8
Mental Health Specialist	MHS	1
Interpersonal Reactivity Index	IRI	28
BRFSS Adverse Childhood Experience (ACE) Module	BRFSS ACE	11
Brief Resilience Scale	BRS	6
Experiences in Close Relationships - Relationship Structures	ECR-RS	9
Multidimensional Assessment of Interoceptive Awareness	MAIA	37
Five Facets of Mindfulness Questionnaire	FFMQ	20
Trauma Exposure and Training	TE	4
Feedback	FE	2

Note: *All items may not actually appear in each survey.

C. DECEPTION - If any deception (withholding of complete information) is required for the validity of this activity, explain why this is necessary and attach debriefing statement.

No deceptive practices will be used.

- D. SUBJECTS
 - Approximate number and ages How Many Subjects: 65 Age Range of Subjects: 18 years and older How Many Normal/Control: n/a Age Range of Normal/Control: 18 years and older
 - 2. Criteria for selection:

Study participants must be either students at MSU or working or volunteering in a victim service profession or organization. All participants must be 18 years or older.

3. Criteria for exclusion:

For the first two cohorts, those who are not undergraduate students at Montana State University will be excluded from data collection. For the third cohort, study participants not working or volunteering in a victim service profession or organization will be excluded from data collection. Anyone who is not 18 years or older will be excluded from all parts of the study.

4. Source of Subjects (including patients):

For cohorts one and two, study participants will be recruited in the classroom. Both Drs. [name] and [name] are popular teachers who attract students interested in issues of trauma and mindfulness. For cohort 3, community contacts, victim service organizations, and community advisory board members will help with recruitment.

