5. Who will approach subjects and how? Explain steps taken to avoid coercion.

Students who choose to enroll in the class will be required to read and work with the content of the course, however, they will not be required to participate in the evaluation survey. We will emphasize in the syllabus and verbally in class, that participation, or nonparticipation, in the survey is absolutely optional and will not count towards their grade in anyway. Victim service providers will be free not to participate and can end participation at any time.

6. Will subjects receive payments, service without charge, or extra course credit? **X Yes** or No (If yes, what amount and how? Are there other ways to receive similar benefits?)

For the first two cohorts, if at least 85% of the students in each class participate in data collection waves one and two, all students will be eligible for some form of extra credit and/or participation in some kind of celebration (such as pizza on the last day of class). All students will be eligible, even if they themselves did not participate. Students who participate in data collection wave three (approximately1 month after class has ended) will receive a \$20 e-gift card. Victim service providers who participate in cohort three will be eligible for MSU continuing education credits and \$20 e-gift cards for each survey.

7. Location(s) where procedures will be carried out.

Cohorts one and two will be carried out in a classroom on campus. Cohort three will be held at a time and place convenient for all the participating victim service providers.

E. RISKS AND BENEFITS (ADVERSE EFFECTS)

1. Describe nature and amount of risk and/or adverse effects (including side effects), substantial stress, discomfort, or invasion of privacy involved.

Some of the questions on the survey will ask about personal and potentially emotional topics. While these questions may cause some discomfort, a list of resources will be provided should participants feel they need to seek help.

While it is not the focus of the study, the survey will ask about alcohol and other drug use. We ask these questions because respondents may be using substances to cope with secondary trauma. To protect participants, identifying information will be separated from their responses and all information will be deidentified when presented or published.

2. Will this study preclude standard procedures (e.g., medical or psychological care, school attendance, etc.)? If yes, explain.

No.

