
3. Describe the expected benefits for individual subjects and/or society.

Survey data will document the prevalence of ST and its correlates. If successful, the intervention will be a useful tool for improving the work lives and psychological health of victim service providers.

- F. ADVERSE EFFECTS
 - 1. How will possible adverse effects be handled?

No adverse effects are expected. If participants become upset during the survey, a list of resources is provided in the consent form.

By investigator(s):

NA

Referred by investigator(s) to appropriate care:

N/A

Other (explain):

N/A

- 2. Are facilities/equipment adequate to handle possible adverse effects? **X Yes** or No (If no, explain.)
- 2. Describe arrangements for financial responsibility for any possible adverse effects.

None. In our view, there is no reasonable concern that a participant would experience any adverse effects.

MSU compensation (explain): NA Sponsoring agency insurance: NA Subject is responsible: NA Other (explain): NA

- G. CONFIDENTIALITY OF RESEARCH DATA
 - 1. Will data be coded? X Yes or No

- 2. Will master code be kept separate from data? X Yes or No
- 3. Will any other agency have access to identifiable data? Yes or **X No** (If yes, explain.)

Workplaces will not have access to providers' data.

4. How will documents, data be stored and protected? Locked file:

Yes, all physical files will be locked in a cabinet and in a locked office on campus.

Computer with restricted password:

Yes, all de-identified digital files will be kept on password-protected computers or stored on a secured server.

Other (explain): N/A

- VIII. Checklist to be completed by Investigator(s)
 - A. Will any group, agency, or organization be involved? Yes or **X No** (If yes, please confirm that appropriate permissions have been obtained.)
 - B. Will materials with potential radiation risk be used (e.g. x-rays, radioisotopes)? Yes or X No
 - 1. Status of annual review by MSU Radiation Sources Committee (RSC). Pending or Approved (If approved, attach one copy of approval notice.)
 - 2. Title of application submitted to MSU RSC (if different).
 - C. Will human blood be utilized in your proposal? Yes or **X No** (If yes, please answer the following)
 - 1. Will blood be drawn? Yes or **X No** (If yes, who will draw the blood and how is the individual qualified to draw blood? What procedure will be utilized?)
 - 2. Will the blood be tested for HIV? Yes or **X No**

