When I have distressing thoughts or images, I judge myself as good or bad, depending what the thought/image is about.	\bigcirc	\bigcirc	\bigcirc	0	\bigcirc
I pay attention to how my emotions affect my thoughts and behavior.	\bigcirc	\bigcirc	\bigcirc	\bigcirc	\bigcirc
I can usually describe how I feel at the moment in considerable detail.	\bigcirc	\bigcirc	\bigcirc	\bigcirc	0
I find myself doing things without paying attention.	\bigcirc	\bigcirc	\bigcirc	\bigcirc	\bigcirc
I disapprove of myself when I have irrational ideas.	\bigcirc	\bigcirc	\bigcirc	\bigcirc	\bigcirc

TE (Trauma Exposure and Training Questions)

Overall, how much of your work involves (directly or indirectly) engaging with traumatized individuals or traumatic material?
◯ A great deal
O A lot
O A moderate amount
◯ A little
O None at all

How much training have you received on primary or secondary trauma (including topics like vicarious trauma, secondary traumatic stress, burnout, and moral distress)?
A great deal
A lot
A moderate amount
A little
None at all

Altogether, how effective were your trainings on primary or secondary trauma (including topics

like vicarious trauma, secondary traumatic stress, burnout, and moral distress)?
C Extremely effective
◯ Very effective
O Moderately effective
Slightly effective
◯ Not effective at all
Do you want more training on secondary trauma (including topics like vicarious trauma, secondary traumatic stress, burnout, and moral distress)?
secondary traumatic stress, burnout, and moral distress)?
secondary traumatic stress, burnout, and moral distress)?
secondary traumatic stress, burnout, and moral distress)? Definitely yes Probably yes
secondary traumatic stress, burnout, and moral distress)? Definitely yes Probably yes Might or might not

FE (Feedback)

Are there any factors affecting your answers that we should know about (e.g., a health issue or language barrier)?

Please provide any other feedback you would like to share.

Identifiers

Thank you for participating in our survey. We would like to email you an Amazon.com eGift Card. To do so, we need you to complete the following questions.

Please allow one week for us to email you the eGift Card. Thanks for your patience with us!

What is your first name?

What is your last name?

What is your phone number (e.g., XXX-XXX-XXXX)?

What is your email address? (This is where we will send your e-gift card.)

Please verify your email address.

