Official Title: Somatic Mindfulness Training for a Healthy Workforce: Student Pilot Sample

NCT Number: NCT04122534

Document Date: 08/08/2019

STATISTICAL ANALYSIS PLAN

For each outcome measure (i.e., STSS, PCL-5), most analyses will simply involve calculating descriptive statistics for each wave of data collection. We are pilot testing materials using a small sample and findings will help inform future statistical designs and power needs.

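### The SAP's per-wave summaries cannot give the within-student change data its power-planning aim needs, and the text does not say how the student code is carried across waves one and two (minor)

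*Combined protocol and SAP*

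**What the plan says.** - **Design (VII.B, first and second cohorts).** Two undergraduate classes, of about 15 and of 35 students, are surveyed early in the semester and again near its end. Of the follow-up the plan says: "A third wave may also be collected approximately one month after the course". The purpose is stated as: "The content and effectiveness of the course will be evaluated using a survey".
- **Incentives (VII.B and VII.D.6).** Waves one and two carry a class-level reward if at least 85% take part, and it is open to non-participants too. The individual card belongs to the last wave: "Students who participate in data collection wave three (approximately1 month after class has ended) will receive a" $20 e-gift card. Providers in the third cohort get a card after each of three surveys.
- **Identifiers page (end of the student survey).** It asks for first and last name, phone and email, and opens: "We would like to email you an Amazon.com eGift Card. To do so, we need you to complete the following questions". The provider survey carries the same page.
- **Survey versions (List of Attachments).** One student version and one provider version are filed, with none specific to a wave. Table 1 lists no study ID or self-made code.
- **Confidentiality (VII.E.1, VII.G.1 and G.2).** Identifying details are to be held apart from answers, and the data are coded. The question "Will master code be kept separate from data" is answered yes.
- **SAP.** For each outcome, with STSS and PCL-5 named, "most analyses will simply involve calculating descriptive statistics for each wave of data collection". It adds that "findings will help inform future statistical designs and power needs".

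**The concern.** The same students are asked the same questions up to three times, so the most informative quantity is change within a student. The SAP describes each wave separately and names no change score, paired summary or correlation.

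Two things are at stake. First, participation is optional, the third wave is provisional, and its incentive differs from that of the first two. Respondents can therefore differ from wave to wave, and a shift between wave means mixes change in students with a change in who answered. Second, a later repeated-measures study needs the SD of change, or equivalently the between-wave correlation, for its sample size. Separate wave summaries supply neither.

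Both gaps can be closed only if each student's waves can be joined. The Identifiers page gives a reason that applies to students at wave three alone, and the text does not say how the master code reaches waves one and two.

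**Working it through.** The plan states no power, correlation, SD or response rate, so it has no figure of its own to reproduce. The check has a textual part and an illustration.

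**1. The passages side by side.**

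| Item | Student waves 1 and 2 | Student wave 3 | Provider waves 1 to 3 |
|---|---|---|---|
| Individual gift card due | No | Yes | Yes |
| Stated reason on Identifiers page fits | No | Yes | Yes |
| Data coded, master code separate | Yes | Yes | Yes |
| How the code is applied is stated | No | No | No |

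The page fits the provider cohort throughout. For students its stated reason fits one wave of three.

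**2. Could demographic items do the linking?** The student survey asks age, sex, race, major, class status, work hours and similar items. If there are K equally likely profiles, the expected share of students with a unique profile is (1 − 1/K)^(n − 1). K is assumed.
- n = 15: 49% at K = 20, 97% at K = 500.
- n = 35: 17% at K = 20, 93% at K = 500.

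Some students could be matched this way, but not dependably, because answers such as age and work hours can change between waves.

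**3. Precision of mean change, waves one to two.** Illustrative n at the 85% reward threshold: 0.85 × 15 rounds up to 13 and 0.85 × 35 rounds up to 30, so n = 43. The within-student correlation r is assumed to be 0.3 to 0.7, with equal SD at both waves.
- Treated as unlinked: 1.96 × √(2/43) = 0.42 SD (95% half-width).
- Linked: 1.96 × √(2(1 − r)/43) = 0.35, 0.30 and 0.23 SD at r = 0.3, 0.5 and 0.7.
- Ratio: 1/√(1 − r) = 1.20, 1.41 and 1.83.

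**4. What a later study would need.** Assume a paired design, a 0.3 SD change, 80% power and two-sided 5%. Pairs = (1.960 + 0.842)² × 2(1 − r)/0.3², rounded up:
- r = 0.3: 123
- r = 0.5: 88
- r = 0.7: 53

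The range is 123/53 = 2.3-fold. Per-wave means and SDs do nothing to narrow it, because r does not appear in them.

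**5. Who answered.** Suppose a fraction p of wave-one respondents answer wave three, and they differ at baseline from the rest by d. The difference between wave means is then off by (1 − p) × d. With p = 0.8 and d = 0.2 SD this is 0.04 SD; with p = 0.5 and d = 0.5 SD it is 0.25 SD. Both p and d are assumed.

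**The case against.** A reader might infer that the plan has no linking key, or that waves one and two cannot be matched. The documents do not support either.

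- VII.G.1 and G.2 state coded data and a separate master code, and VII.E.1 presupposes that identifiers are collected. What is missing is how the code is applied, not the code.
- Only one student version is filed and it contains the Identifiers page, so the plainest reading is that name and email are requested at every wave. The Table 1 note "All items may not actually appear in each survey" is tied to asterisked rows. The Identifiers page is not a row of that table, so the note does not show that the page is dropped at any wave.
- Demographic items could match some students in classes this small.
- Consent and other pages are not in the available text and may describe a key. A personal survey link would also serve.

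It can also be said that a small descriptive pilot needs no linkage for what its SAP mainly plans, and that the SAP names no paired successor study. The first part is true: per-wave statistics can be produced without linkage. The word 'most' also leaves room for further analyses, though none is named.

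These arguments reduce the survey question to a missing detail and a wording mismatch. They do not answer the SAP point. Even with perfect linkage, the analyses it describes would not yield the SD of change or the correlation, and the SAP itself names power planning as a use of the findings.

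**Conclusion.** The concern holds as a minor point. The SAP's stated analyses stop short of its own stated use. Separate wave summaries cannot distinguish change in students from a change in respondents, and they omit the quantities that drive the size of a later repeated-measures study. Alongside this, the student Identifiers page gives a purpose that fits wave three only, and the available text does not say how the existing code is applied earlier.

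The figures are illustrations, not losses shown to occur in this plan: an interval 1.2 to 1.8 times wider if waves must be treated as unlinked, a 2.3-fold range in future sample size, and a 0.04 to 0.25 SD distortion from selective response at wave three. They rest on the assumed correlations, response rates, baseline differences and target effect. The part due to unlinkable data is zero if a key already works at every wave. What then remains is only that the SAP does not say the linked data will be summarised.

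**What to change.** **In the SAP**, for STSS and PCL-5, add:
- the number of students linked for each pair of waves;
- the mean and SD of change among them;
- the within-student correlation;
- wave-one scores of students with and without later waves.

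**To support this:**
- confirm in VII.G that the existing code is collected or attached at every student wave, and how (a self-generated code or a personal survey link would do);
- reword the student Identifiers page so that linkage is the stated purpose at waves one and two, and the gift card is mentioned at wave three only.

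The cost is a few sentences in the SAP, one in VII.G and a small edit to one survey page. The survey change can go on the same minor-modification form that was used to add the Self-Compassion Scale. It needs no extra participants, waves or rewards. If the code is not already in use, it has to be in place before wave one, because responses collected without it may not be matchable later. If it is, one sentence settles that part.
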